A suppository will be placed rectally by a member of the surgical team at the conclusion of surgery, prior to departure from the OR and awakening from anesthesia. Post-operative placement was selected to minimize interaction with intraoperative anesthetic and analgesic medications, to maximize peak plasma concentrations and therapeutic efficacy of Belladonna alkaloids and Opium within the immediate postoperative period, and control for variation in procedure length between study participants. The nurses caring for the patient postoperatively will be blinded to which suppository the patient did receive, but will be made aware that the patient had received a suppository containing either glycerin or one containing belladonna 16.2mg and opium 60mg, equivalent to approximately 6mg of morphine. These nurses will be educated about potential side effects of Belladonna & Opium suppositories, and of potential drug interactions; they will be asked to document and to inform the covering provider of the occurrence of any such adverse effects. Patients remaining in the hospital overnight following their surgery will undergo a postoperative exam by a resident physician familiar with the study protocol and familiar with potential side effects of the B&O suppository; this physician will inquire about and document the presence of any such side effects. Standard of care at Mercy Medical Center is for nurses to assess patient’s postoperative pain by visual analog scale at regular time intervals. Data regarding patients’ visual analog pain scores for the first 12 hours following surgery will be extracted from the electronic medical record and analyzed by the research team. PO and IV narcotic use in IV morphine equivalents, PO and IV NSAIDs, and PO and IV antiemetic use will also be assessed over the first 12 following surgery, this data is to be extracted from the electronic medical record and analyzed by the research team. Study surveillance will not extend beyond the duration of the participant's postoperative hospitalization, usually less than 24 hours.

The costs of the Belladonna & Opium Suppettes and glycerin rectal suppositories used in this study will be covered by University of Maryland Medical Center, Department of Obstetrics, Gynecology and Reproductive Sciences as a supported resident research project. The costs of glycerin suppositories will be covered by Mercy Medical Center Pharmacy.

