The primary hypothesis of the study is that the use of a B&O rectal suppository is associated with decreased postoperative pain and nausea following total laparoscopic or robot-assisted hysterectomy. The visual analog scale (VAS) to be used for assessment of postoperative pain has been demonstrated to be linear in the setting of mild-to-moderate pain [9], such that a 15% decrease in VAS score corresponds to a 15% decrease in subjectively experienced pain. Minimal clinically significant difference in score on the VAS has been shown to occur at approximately 11-14 mm regardless of pain severity [10]. Sample size calculation is based on VAS pain scores following laparoscopic hysterectomy as reported by Ghezzi, et al. [11]. Sample size is set at 65 patients per group (total trial enrollment of 130 patients) with a goal of detecting a 30% decrease in mean VAS score with 80% power, using $p = 0.05$ as a criteria for statistical significance, and accounting for a rate of up to 15% for trial withdrawal, incomplete data, and loss-to-follow-up [12].

For statistical methodology, patient characteristics for the two study arms will be analyzed using a two-sided Student's t-test for continuous variables, or a χ^2 test for categorical variables and proportions. To assess for clinical superiority of the B&O suppository intervention, one-sided Student's t-test (for continuous outcomes) or a one-sided Fisher's Exact test (for categorical outcomes) will be used. One-sided tests are to be used since the addition of B&O is not expected to increase pain, narcotic use, recovery time, or need for rescue anti-emetics a priori. Fisher's Exact test was chosen as a more conservative measure for assessing outcomes, and due to the availability of a one-sided test. A linear regression will be performed on the outcome of PACU discharge readiness time using several different model specifications in order to check for robustness of results.

Bibliography

- [1] CEO of Amerifit Brands, Inc., Nov 7, 2007 Gail T. Costello to Cyrill Siewert.
<http://www.fda.gov/ICECI/EnforcementActions/WarningLetters/2007/ucm076570.htm>.
- [2] Alexander, Thomas J. Lauterio, and Matthew W. Davis Nasr, "Unapproved drugs in the United States and the Food and Drug Administration," *Advances in therapy*, vol. 28, no. 10, pp. 842-856, October 2011.

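### The primary hypothesis joins pain and nausea with no designated primary endpoint, success rule or multiplicity control, so neither the 5% error rate nor the 80% power is tied to a defined claim

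*Combined protocol and SAP*

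**What the plan says.** The document has no numbered sections; the relevant text is in three places.

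- **Hypothesis and sample size paragraph.** "The primary hypothesis of the study is that the use of a B&O rectal suppository is associated with decreased postoperative pain and nausea". The same paragraph says "Sample size calculation is based on VAS pain scores following laparoscopic hysterectomy", and gives 65 per group for a 30% fall in mean VAS with 80% power and up to 15% losses, "using $p = 0.05$ as a criteria for statistical significance". This is the only significance level in the document.
- **Statistical methodology paragraph.** For superiority, a "one-sided Student's t-test (for continuous outcomes) or a one-sided Fisher's Exact test (for categorical outcomes) will be used". The reason given is that "the addition of B&O is not expected to increase pain, narcotic use, recovery time, or need for rescue anti-emetics a priori", which names four outcomes. PACU discharge readiness time also gets a linear regression, "using several different model specifications in order to check for robustness of results".
- **Suppository placement and data collection paragraph.** "Data regarding patients’ visual analog pain scores for the first 12 hours following surgery will be extracted from the electronic medical record", and "PO and IV narcotic use in IV morphine equivalents, PO and IV NSAIDs, and PO and IV antiemetic use will also be assessed" over the same period. No time point or summary of the VAS scores is fixed.

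Nowhere is an outcome labelled primary or secondary, and there is no rule for combining pain and nausea.

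**The concern.** A hypothesis about two things can be confirmed in two ways. If a significant result on either one counts, there are two chances of a false positive and 5% is no longer the error rate. If both must be significant, the error is protected but the trial can fail on either one, and the power calculated for pain alone does not describe it. The plan leaves this choice open, so it could be made after the results are known.

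The same gap extends to the outcomes outside the hypothesis. Narcotic use and recovery time sit beside pain and antiemetic use in the reason for one-sided tests, with nothing to separate confirmatory from supportive results.

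Nausea has a further difficulty. It is in the title and the primary hypothesis, yet no nausea score or incidence is defined as an efficacy outcome. A conclusion about nausea would in fact be one about drug use.

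**Working it through.** **Inputs from the protocol.** Level 0.05; one-sided outcome tests; 65 per group; up to 15% losses; 80% power for a 30% fall in mean VAS; four named outcomes (pain, narcotic use, recovery time, rescue antiemetics).

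**Assumptions.** Each outcome is tested at 0.05, since no other level or adjustment appears. Correlations between tests and antiemetic rates are not in the document, so ranges are shown.

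**1. The plan's own figure.** 65 × 0.85 = 55.25, so about 55 evaluable per group (55 / 0.85 = 64.7, rounded up to 65). The VAS mean and SD are not given, so 65 can be neither confirmed nor refuted. Solving n = 2(SD/mean)²(z_α + z_β)² / 0.30² at n = 55:

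- One-sided: SD/mean = 0.30 × √27.5 / (1.645 + 0.842) = 0.63.
- Two-sided: SD/mean = 0.30 × √27.5 / (1.960 + 0.842) = 0.56.

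The figure is internally plausible, and it concerns pain only.

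**2. Either or any outcome suffices.** For k independent tests, the chance of at least one false success is 1 − 0.95^k. For correlated tests, it is one minus the multivariate normal probability that all k statistics fall below 1.645.

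| Outcomes | Independent | r = 0.3 | r = 0.5 | r = 0.7 | r = 0.9 |
|---|---|---|---|---|---|
| 2 (pain, nausea) | 9.75% | 9.3% | 8.8% | 8.0% | 6.8% |
| 4 (all named) | 18.5% | 16.4% | 14.4% | 12.0% | 8.8% |

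If antiemetic use is analysed as yes/no, the plan's one-sided Fisher's Exact test applies. Its actual size at 55 per group is 2.6-3.5% for event rates of 10-60%. At rates of 30-40% the size is about 3.2%, so with an independent pain test the two-outcome figure is 1 − 0.95 × 0.968 = 8.0%, about 8%.

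**3. Both pain and nausea required.** The error cannot exceed 5%. With no effect on either outcome it is 0.05² = 0.25% if independent, and 1.2% at r = 0.5. Joint power under independence is 0.80 × the power of the one-sided Fisher test at 55 per group:

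| Assumed antiemetic use, placebo v B&O | Fisher power | Joint power |
|---|---|---|
| 40% v 30% | 22% | 18% |
| 40% v 20% | 68% | 54% |
| 50% v 25% | 81% | 65% |
| 60% v 30% | 92% | 74% |

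At 40% v 20%, correlations of 0.3 to 0.7 raise joint power to 57-63%. It can never exceed the power for pain alone.

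**4. Cost of splitting alpha instead.** At 0.025 for each of pain and nausea, and the SD/mean ratios from step 1, pain alone needs 70 evaluable per group one-sided (70 / 0.85, rounded up, = 83) or 67 two-sided (67 / 0.85, rounded up, = 79). Staying at 55 evaluable, power for pain falls to about 70-71%.

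**The case against.** The strongest reply is that the hypothesis says pain and nausea. Read literally, both are required and the error is not inflated at all. Sizing on VAS also makes pain the implied primary outcome. Both points stand, and they limit the finding. But they point to different claims, one joint and one about pain alone, and the plan does not choose between them.

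A reader might infer more than the document supports:

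- **That the trial's false-success rate is far above 5%.** This needs an any-outcome success rule, which the document does not state. For pain and nausea alone, the conservative Fisher test and any positive correlation reduce the excess further.
- **That five outcomes, plus VAS at each time, are all tested, giving 22.6% or more.** The reason for one-sided tests names four. NSAID use is listed only as data to be assessed, separate VAS tests at each time are not specified, and the regressions are described as robustness checks. The extra outcomes are not part of the primary hypothesis either.
- **That the stated 80% power is wrong.** It is stated for VAS only, so a lower joint power contradicts no figure in the plan.
- **That nausea is never measured.** Nausea and vomiting are on the side-effect list that nurses are asked to document, and a resident asks overnight patients about side effects. This is safety recording rather than a systematic efficacy measure.
- **That antiemetic use is a biased stand-in.** The postoperative nurses are to be blinded. Scopolamine patches are pre-operative, and randomization balances them in expectation. Antiemetic use is indirect, but these points do not show it to be biased between the arms.

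**Conclusion.** The concern holds in a conditional form. What is certain from the text is the omission: a two-part primary hypothesis, a one-part sample size, and nothing that defines success or controls multiplicity. Its size depends on the rule eventually applied. The error is about 8-10% if either pain or nausea suffices and the tests are independent. It reaches 18.5% at most if any of four independent outcomes suffices. It does not exceed 5% if both pain and nausea are required, at the price of a joint power that the plan never calculated. The error figures rest on testing each outcome at one-sided 0.05, and the correlated figures on assumed correlations. The joint power range rests on assumed antiemetic rates and independence. This should be corrected, but it does not invalidate the design.

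**What to change.** In the hypothesis and statistical methodology paragraphs, before treatment codes are broken:

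1. Name one VAS pain summary over a fixed window as the sole primary endpoint at 0.05, for example the time-weighted mean over the first 12 hours, and restate the primary hypothesis for pain. Say how patients discharged before the window ends are handled, since surveillance stops with the hospital stay.
2. Test the secondaries in a fixed order, each at 0.05 and only while the preceding test is significant: any rescue antiemetic use (yes/no), narcotic use, PACU discharge readiness time.
3. Treat NSAID use and individual VAS times as exploratory.
4. Word the nausea conclusion as rescue antiemetic use.

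The time-weighted mean and this order are one reasonable choice. A defined rule requiring both pain and nausea would also settle the error rate, but would need its own power calculation.

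The cost is wording only: 65 per group is unchanged and no new data are needed. Nausea loses its place in the primary hypothesis, and a secondary that follows a failed test can only be described. A nurse-charted nausea score would support a direct nausea claim, but it means new prospective charting in a study built on routine records, and this fix does not depend on it.

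### One-sided Fisher's exact test uses at most about 3.5–4.1% of the stated 5% at this trial's size; one-sided Boschloo's exact test keeps the 5% guarantee and usually adds a few points of power at no cost

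*Combined protocol and SAP*

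**What the plan says.** The relevant text is in the last two unnumbered paragraphs before the bibliography of the combined protocol and SAP, on sample size and on statistical methods.

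- Continuous efficacy outcomes get a one-sided Student's t-test. For categorical ones, the plan names Fisher's, again one-sided: "Exact test (for categorical outcomes) will be used".
- The choice of Fisher is explained: "Exact test was chosen as a more conservative measure for assessing outcomes, and due to the availability of a one-sided test".
- The reason for one-sided testing also names the outcomes: "One-sided tests are to be used since the addition of B&O is not expected to increase pain, narcotic use, recovery time, or need for rescue". That sentence ends by specifying antiemetic medication, and this last outcome is the one most naturally analysed as yes/no.
- The design targets mean VAS being lower by 30%, "with 80% power, using $p = 0.05$ as a criteria for statistical significance". It allows for loss of up to 15% and arrives at 65 per group.

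No event rate, target difference or power is stated for any categorical outcome.

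**The concern.** Neither stated reason singles out Fisher. Boschloo's exact test also has a one-sided form. Being conservative protects the type I error only down to the level the plan chose. Below that level it gives up power and adds nothing to the 5% guarantee.

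Fisher's shortfall comes from discreteness. The test conditions on the total number of events, so only a few p-values are attainable for each total, and the largest one not exceeding 0.05 is often well below it. The size of the shortfall depends on the sample size and the event rate, and nobody sets it deliberately.

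What is at stake is a somewhat higher chance of missing a real effect on a categorical outcome such as need for rescue anti-emetics. Nausea is part of the primary hypothesis, and the plan describes no nausea scale, so that outcome may carry weight.

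**Working it through.** **Inputs from the documents.** 65 per group, equal allocation, up to 15% loss, criterion 0.05. The sample-size sentence does not state sidedness; I read 0.05 as one-sided because the efficacy tests are one-sided.

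**Assumed inputs.** All event rates below. The documents give none.

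**The plan's own figure.** The loss step is consistent: 55 / (1 − 0.15) = 64.7, rounded up to 65. So 55 per arm is the evaluable number at full loss and 65 at no loss. The VAS mean and SD behind the 55 are not given (only a cited source), so the 65 can be neither confirmed nor refuted. It concerns a t-test outcome and is not in question here.

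**Method.** List every table (x_T, x_C) for n per arm, with s = x_T + x_C.

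- One-sided Fisher p-value: P_F = Σ over k ≤ x_T of C(n,k)·C(n,s−k) / C(2n,s). Reject if P_F ≤ 0.05.
- True size at common rate π: the sum of Bin(x_T; n, π)·Bin(x_C; n, π) over rejected tables, maximised over π. Power is the same sum with the two arms' own rates.
- Boschloo: reject if P_F ≤ c, where c is the largest cutoff whose maximum size stays at or below 0.05. The cutoff is 0.063 at n = 55 and 0.068 at n = 65. Both exceed 0.05, so every table that Fisher rejects is also rejected by Boschloo.

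**True size at nominal one-sided 0.05.**

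| n per arm | Fisher, maximum | Fisher, mean over rates 10–90% | Boschloo, maximum |
|---|---|---|---|
| 55 | 3.48% | 3.1% | 4.99% |
| 60 | 4.12% | 3.4% | 4.9% |
| 65 | 3.51% | 3.2% | 4.90% |

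The Fisher maxima are ceilings. At a 5% event rate its size is 1.3% (n = 55) and 1.7% (n = 65).

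**Power, Fisher v Boschloo.**

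| Assumed rates (placebo v B&O) | n = 55 | n = 65 |
|---|---|---|
| 50% v 30% | 62.1% v 69.1% | 69.0% v 74.5% |
| 40% v 20% | 67.8% v 72.1% | 75.8% v 80.6% |
| 60% v 40% | 61.7% v 67.7% | 67.4% v 73.6% |
| 30% v 15% | 51.2% v 56.3% | 58.9% v 65.1% |

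The differences in this table run from 4.3 to 7.0 points. The gain shrinks towards zero when power is already very high. It also varies with n: at 60 per arm it is only 0.2 point for 60% v 40% (68.1% v 68.3%) and about 3 points for 50% v 30%.

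**Patient equivalent.** To match Boschloo's power at 55 per arm, Fisher needs 59 to 68 per arm across the rate pairs tried (4 to 13 more). To match it at 65, Fisher needs 71 to 77 (6 to 12 more). When both tests are sized for 80% power, Fisher needs 4 to 9 more. A fair summary is roughly 5–10 per arm.

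**At 0.025 in one direction, n = 55.** For 50% v 30%, power is 49.1% v 55.5%, so the gap remains.

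**Two-sided software versions, arms of 65 and 60.** For 21/65 v 30/60, standard two-sided Fisher gives p = 0.048, while a two-sided Boschloo p-value formed by doubling the smaller one-sided one gives 0.051. For 51/65 v 55/60 the values are 0.048 and 0.055. The dominance is therefore a one-sided result.

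**The case against.** The strongest reply is that nothing here is wrong. Fisher's test is valid, it is named in advance, and its conservatism is disclosed and intended. A margin below 5% might even be welcome in a plan that tests several outcomes one-sided at 0.05 with no stated adjustment for multiplicity. That the choice is valid and disclosed stands. The multiplicity argument does not rescue it: the shortfall shifts with sample size and event rate, so it is not a controlled adjustment. If multiplicity is the worry, it should be handled directly.

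The second reply also stands: every power figure depends on assumed rates, and power is saw-toothed in n. For 50% v 30%, Fisher already reaches 68.5% at 60 per arm, and the next five patients bring it only to 69.0%. A reader might infer a flat loss of about 10 patients per arm, or a true level of 3.5% throughout. The first is near the top of the summary range. The second is the ceiling at 55 and 65 per arm, while at 60 the ceiling is 4.1%.

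A reader might also infer that the nausea half of the primary hypothesis rests on this test. That is plausible but not stated: the protocol says that antiemetic use over the first 12 hours will be assessed, and does not define it as a yes/no outcome.

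**Conclusion.** The point holds as an avoidable loss of efficiency. At 55–65 evaluable per arm, one-sided Fisher's maximum size is about 3.5–4.1%. One-sided Boschloo keeps the same exact 5% ceiling, can never reject less often, and usually gains about 4–7 power points (range about 0–7), or roughly 5–10 patients per arm. The size figures depend only on n and a one-sided 0.05; the power and patient figures also depend on assumed event rates.

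The documents do not support reading this as an error in the plan, an inflated type I error, or a fault in the 65 per group. Nor may the dominance claim be carried over to the common two-sided versions of the tests. The change is worth making because it costs nothing, but the trial is sound on this point without it.

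**What to change.** Before unblinding, amend the statistical methods paragraph:

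1. Replace one-sided Fisher with one-sided Boschloo's exact test, at the same alpha, for categorical efficacy outcomes.
2. Delete the rationale that Fisher is more conservative and available one-sided.
3. Report the risk difference with a named interval, for example the Miettinen–Nurminen score interval. A 90% two-sided interval corresponds to one-sided 0.05 (1 − 2 × 0.05). State that it may disagree slightly with the exact p-value near the boundary.
4. If testing becomes two-sided, apply one-sided Boschloo at 0.025 in each direction, and do not claim that it always dominates the standard two-sided Fisher test.

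Cost: a few sentences in the plan and a check that the chosen software gives both the test and the interval, since some routines return only a statistic and p-value. No extra patients or data are needed.

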Neither you, nor the patient will be informed which of the two drugs the patient received. Please treat your patient with routine post-operative care, recognizing that they may have already received the equivalent of 6mg of morphine immediately prior to departure from the OR.

Common side effects of B&O suppository are related to anticholinergic activity and include dry nose, mouth, throat, skin, and constipation. Serious side effect are estimated at less than 1% occurrence and include orthostatic hypotension, ventricular fibrillation, tachycardia, palpitation, confusion, drowsiness, headache, loss of memory, fatigue, ataxia, CNS depression, rash, antidiuretic hormone release, bloated feeling, nausea, vomiting, biliary tract spasm, dysuria, urinary retention, urinary tract spasm, increased intraocular pain, blurred vision, weakness, respiratory depression, histamine release, physical and psychological dependence, and diaphoresis. Please notify the GYN resident/fellow if you suspect that your patient is experiencing any of these serious side effects.
